9.4. Vital Signs

Values at each scheduled visit, change, and percentage change from baseline for vital signs, including systolic blood pressure, diastolic blood pressure, pulse, temperature, respiratory rate, and weight will be summarized descriptively.

Normal ranges for vital sign values are defined in [Table 4](#). For participants exhibiting vital sign abnormalities, the abnormal values will be listed along with their assigned treatment group.

Alert vital signs are defined as an absolute value outside the defined normal range and percentage change greater than 25%. Note that the definition of alert vital signs does not apply for body temperature and weight. The abnormal values for participants exhibiting alert vital sign abnormalities will be listed.

Table 4: Normal Ranges for Vital Sign Values

Parameter	High Threshold	Low Threshold
Systolic blood pressure	≤ 155 mmHg	≥ 85 mmHg
Diastolic blood pressure	≤ 100 mmHg	≥ 40 mmHg
Pulse	≤ 100 bpm	≥ 45 bpm
Temperature	$\leq 38^{\circ}\text{C}$	$\geq 35.5^{\circ}\text{C}$
Respiratory rate	≤ 24 breaths/min	≥ 8 breaths/min

9.5. Electrocardiograms

Twelve-lead ECGs including PR, QT, QRS, RR, and QTc intervals will be obtained for each participant during the study. Values at each scheduled visit, change, and percentage change from baseline will be summarized for each ECG parameter. Baseline will be determined as the average of all nonmissing values before the first administration of parsaclisib, placebo or ruxolitinib.

Normal ranges for ECG values are defined in [Table 5](#). ECG values will also be considered abnormal if the absolute percentage change from baseline is more than 25% (30% for QRS interval). Participants exhibiting ECG abnormalities will be listed with study visit and by assigned treatment group. Abnormal values for participants with alert ECG values, defined as both the absolute value and the percentage change from baseline being outside normal ranges, will be identified and listed. Outliers of QT and QTc values, defined as absolute values ≥ 500 milliseconds, ≥ 480 milliseconds, and ≥ 450 milliseconds for each parameter, or change from baseline ≥ 30 milliseconds and ≥ 60 milliseconds for each parameter, will be summarized.

Table 5: Normal Ranges for Electrocardiogram Intervals

Parameter	High Threshold	Low Threshold
PR	≤ 220 ms	≥ 75 ms
QT	≤ 500 ms	≥ 300 ms
QRS	≤ 120 ms	≥ 50 ms
QTc	≤ 450 ms	≥ 295 ms
RR	≤ 1330 ms	≥ 600 ms

Twelve-lead ECGs will be obtained for each participant during the study. Electrocardiogram abnormalities, both at baseline and postbaseline visits, will be tabulated by treatment group. Incidences of abnormalities and a description of the abnormality will be listed with study visit and assigned treatment group.

10. INTERIM ANALYSES

10.1. Overview of Interim Analyses

There will be 2 planned interim analyses conducted for this study. The first interim analysis will be conducted when the first 100 of the planned randomized participants (approximately 50 in each treatment group) reach Week 12 assessments of spleen volume and MFSAF TSS or discontinue from treatment. The first interim analysis is to test Week 12 spleen volume and MFSAF TSS for futility. An HSD ([Hwang et al 1990](#)) with $\gamma = 0$ will be used to determine the nonbinding futility boundary for spleen volume and MFSAF TSS. The study will be terminated early for futility if either the spleen volume or the MFSAF TSS endpoints cross the futility boundary. Based on the results of this interim analysis, the DMC may recommend to terminate the study, continue the study with no changes to enrollment, or continue the study with no further enrollment permitted until review of the second interim analysis.

The second interim analysis will be conducted when the first 220 randomized participants (approximately 110 in each treatment group) reach Week 12 assessments of spleen volume and MFSAF TSS or discontinue from treatment. The second interim analysis is for the efficacy check at 1-sided alpha of 10%. The study will continue if both spleen volume and MFSAF TSS endpoints are positive. The DMC may recommend to either terminate the study for lack of efficacy or continue the study, based on the results of this analysis.

[figure not shown]
At both interim analyses, MFSAF TSS will be tested only if spleen volume passes the futility/efficacy check.

10.2. Derivations and Calculations for Interim Analyses

For the first analysis of futility, the gamma spending function with spending parameter equal to 0 will be used to allocate beta-spending based on a Type II error of 0.16 for spleen volume reduction and 0.2 for MFSAF TSS under the alternative hypothesis. [Figure 1](#) shows that the beta spending function allocates minimal beta for the first interim analysis.

As no formal decision for efficacy will be made based on the efficacy check in the second interim analysis, no alpha will be spent.

Figure 1: Beta Spending

10.3. Guidelines for Decision Rule

[Table 6](#) and [Table 7](#) provide the projected stopping rules if the interim analyses are conducted at the projected number of participants.

Table 6: Interim Analysis for Spleen Volume With HSD (0)

Number of Participants	Interim Analysis 1		Interim Analysis 2		Final Analysis	
	100		220		440	
Decision Outcome	Stop for Futility	Continue to Test MFSAF TSS	Stop for Lack of Efficacy	Continue to Test MFSAF TSS	Do Not Reject Null Hypothesis	Reject Null Hypothesis
Z-statistic	≤ 0.18	> 0.18	≤ 1.28	> 1.28	≤ 1.96	> 1.96
One-sided p-value	≥ 0.43	< 0.43	≥ 0.10	< 0.10	≥ 0.025	< 0.025
Parsaclisib + ruxolitinib response rate ^a for low platelet	$\leq 17.8\%$	$> 17.8\%$	$\leq 23.0\%$	$> 23.0\%$	$\leq 23.4\%$	$> 23.4\%$
Parsaclisib + ruxolitinib response rate ^a for normal platelet	$\leq 42.0\%$	$> 42.0\%$	$\leq 50.0\%$	$> 50.0\%$	$\leq 50.5\%$	$> 50.5\%$

^a Assumes spleen volume response rate for 50 to $< 100 \times 10^9/\text{L}$ inclusive or $\geq 100 \times 10^9/\text{L}$ platelet is 17.2% and 41.0% in placebo plus ruxolitinib.

Table 7: Interim Analysis for MFSAF TSS With HSD (0)

Number of Participants	Interim Analysis 1		Interim Analysis 2		Final Analysis	
	100		220		440	
Decision Outcome	Stop for Futility	Continue to Interim Analysis 2	Stop for Lack of Efficacy	Continue to the Final Analysis	Do Not Reject Null Hypothesis	Reject Null Hypothesis
Z-statistic	≤ 0.18	> 0.18	≤ 1.28	> 1.28	≤ 1.96	> 1.96
One-sided p-value	≥ 0.43	< 0.43	≥ 0.10	< 0.10	≥ 0.025	< 0.025
Parsaclisib + ruxolitinib response rate ^a for low platelet	$\leq 35.4\%$	$> 35.4\%$	$\leq 42.8\%$	$> 42.8\%$	$\leq 43.6\%$	$> 43.6\%$
Parsaclisib + ruxolitinib response rate ^a for normal platelet	$\leq 46.9\%$	$> 46.9\%$	$\leq 54.6\%$	$> 54.6\%$	$\leq 55.5\%$	$> 55.5\%$

^a Assumes TSS response rate for 50 to $< 100 \times 10^9/\text{L}$ inclusive or $\geq 100 \times 10^9/\text{L}$ platelet is 34.5% and 45.9% in placebo plus ruxolitinib.

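### The Interim Analysis 1 response-rate thresholds correspond to Z of about 0.10, not the Z 0.18 printed beside them, and SAP 10.2 should state the beta allocated at that look

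*SAP*

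**What the plan says.** SAP 10.1 places Interim Analysis 1 at the first 100 randomized participants ("approximately 50 in each treatment group") and Interim Analysis 2 at the first 220 ("approximately 110 in each treatment group"). The first look uses a nonbinding HSD futility boundary with gamma 0. The second is a check at one-sided 10%.

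SAP 10.2 says that "the gamma spending function with spending parameter equal to 0 will be used to allocate beta-spending". It sets the total beta at 0.16 for the spleen endpoint and 0.20 for the symptom endpoint. It adds that Figure 1 "shows that the beta spending function allocates minimal beta for the first interim analysis".

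SAP 10.3 introduces Tables 6 and 7, which "provide the projected stopping rules if the interim analyses are conducted at the projected number of participants". For both endpoints the Interim 1 column gives Z 0.18 and one-sided p 0.43. Below these it gives the rates in the parsaclisib arm that mark the boundary: 17.8% (low platelets) and 42.0% (normal) for spleen volume, and 35.4% and 46.9% for TSS. Footnotes fix the control rates at 17.2%/41.0% and 34.5%/45.9%. Protocol 10.5, Tables 19 and 20, carries the same figures.

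**The concern.** Within each Interim 1 column, the Z, p and rate rows should describe one boundary on three scales. The rate rows sit only 0.6 to 1.0 percentage points above control, which looks too close for Z 0.18 with 50 per arm. These figures illustrate the point at which the trial may stop for futility on either endpoint, and they appear in both governing documents, so they should agree.

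A related doubt concerns the beta sentence. HSD with gamma 0 spends beta in proportion to information, so a look well into the information scale takes a substantial share. A reader who relies on the word minimal could misjudge what the first look costs, and the text gives neither the amount nor the information fraction needed to work it out.

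**Working it through.** **Inputs.** The arm sizes are 50, 110 and 220 (SAP 10.1 and Tables 6 and 7). Control and threshold rates come from SAP Tables 6 and 7. Total beta is 0.16 and 0.20, with gamma 0 (SAP 10.2). The low-platelet share is not given; 15% is used for illustration and 0 to 50% as the range.

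**1. Reproduce the printed Z.** Take two looks at 100 and 220, a nonbinding futility boundary, a one-sided 10% test at 220 (Z 1.2816), and linear spending at fraction 100/220.
- Beta at look 1: 0.16 × 100/220 = 0.0727 (spleen); 0.20 × 100/220 = 0.0909 (TSS).
- The drift at 220 that makes total beta 0.16 or 0.20 (bivariate normal) is 2.413 or 2.255. Multiplying by √(100/220) gives 1.627 or 1.520 at look 1.
- Boundary = drift at look 1 + Φ⁻¹(beta at look 1): 1.627 − 1.456 = **0.171** (spleen); 1.520 − 1.335 = **0.185** (TSS). One-sided p is 0.43 for both.

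The printed Z 0.18 and p 0.43 are therefore reproduced. Using 100/440 gives a negative boundary, about −0.28 to −0.39 depending on how the later looks are set up.

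**2. Z implied by the printed rates.** The stratified CMH statistic without continuity correction, with n_s per arm in platelet stratum s, is Z = Σ(n_s/2)(p_T − p_C) / √Σ(n_s/2) p̄(1 − p̄). At a 15% low-platelet share, n_s/2 is 3.75 (low) and 21.25 (normal).
- Spleen: numerator 3.75 × 0.006 + 21.25 × 0.010 = 0.235. Variance 3.75 × 0.175 × 0.825 + 21.25 × 0.415 × 0.585 = 5.700. Z = 0.235/2.388 = **0.098**.
- TSS: numerator 3.75 × 0.009 + 21.25 × 0.010 = 0.246. Variance 3.75 × 0.3495 × 0.6505 + 21.25 × 0.464 × 0.536 = 6.138. Z = 0.246/2.477 = **0.099**.

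Over shares of 0 to 50% the range is 0.091 to 0.101 (spleen) and 0.097 to 0.100 (TSS), so one-sided p is about 0.46. Rounding in the printed rates widens this only to 0.07 to 0.11. About 165 per arm would be needed for these rates to give 0.18.

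**3. The other columns under the same formula (15% share).**

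| | Stated Z | Spleen | TSS |
|---|---|---|---|
| Interim 1 | 0.18 | 0.10 | 0.10 |
| Interim 2 | 1.28 | 1.30 | 1.29 |
| Final | 1.96 | 1.95 | 2.00 |

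Only Interim 1 fails, so the choice of formula is not the cause.

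**4. Rates that match.** Applying a common odds ratio to the control rates and solving for Z at a 15% share gives:
- Z = 0.10: 17.8%/42.0% and 35.4%/46.9%, which are all four printed cells.
- Z = 0.18: **18.3%/42.8%** and **36.2%/47.7%**.

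The gaps are 0.5, 0.8, 0.8 and 0.8 percentage points. At most this is 0.008 × 50 = 0.4 of a responder per arm.

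**5. Beta allocated at Interim 1 under gamma 0.**

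| Information fraction | Spleen | TSS | Share of total |
|---|---|---|---|
| 100/220 | 7.3% | 9.1% | 45% |
| 100/440 | 3.6% | 4.5% | 23% |

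**The case against.** The strongest reply is that the rate row is not a stopping rule. The tables are labelled as projections, and the rates hold only at the footnoted control rates, which observed data will not match exactly. SAP 10.1 derives the boundary from HSD(0), the Z and p rows agree with each other, and the boundary is nonbinding. All of this stands. A reader might infer that the DMC has been given two rival futility lines. The documents do not support that: there is one usable boundary and a miscalculated illustration of it.

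A reader might also treat Z as continuous and conclude that the two cutoffs would disagree in about 1% of trials under the design effect and 3% under the null. With 50 per arm, one responder is 2 percentage points, so Z moves in larger steps than the gap. In a 40,000-run simulation with exactly 50 per arm, balanced within platelet strata, Z 0.10 and Z 0.18 stopped the same trials. When arm counts could differ by up to one within strata, a result fell between them in 0.6 to 0.9% of trials under the design effect and 1.6 to 2.3% under the null.

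On beta, minimal has no numeric definition and the figure it describes is not in the public copy, so the sentence cannot be called false. The information fraction is also inferred, not stated. What remains is that 23% of the total, let alone 45%, is hard to describe as minimal.

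Finally, it is tempting to quote the chance of stopping at Z 0.18 under the design rates as the beta spent. By normal approximation at a 15% share that chance is about 6.7% (spleen) and 8.0% (TSS); simulation at 14% gives 5.4% and 6.8%. These figures apply Week 24 rates to a Week 12 look and one rounded Z to both endpoints. They are not what the spending function allocates.

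**Conclusion.** The Interim 1 rate cells are wrong in all four tables. They match Z of about 0.10 and p of about 0.46, against the printed 0.18 and 0.43. The Z and p rows follow from the stated design, so the boundary itself needs no change. This is a consistency error in printed decision figures with very little effect on stopping, and it leaves alpha, power and the endpoints untouched.

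The beta wording is imprecise. The allocation that goes with Z 0.18 is 7.3% and 9.1%, 45% of each endpoint's Type II allowance, and the SAP should say so.

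The cell finding assumes 50 per arm and a test stratified by platelet count, and holds for any low-platelet share from 0 to 50%. The identification of 100/220 rests on its reproducing Z 0.18 when 100/440 does not.

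**What to change.** - In SAP Tables 6 and 7 and Protocol Tables 19 and 20, replace the Interim 1 rates with about 18.3%/42.8% (spleen) and 36.2%/47.7% (TSS), recomputed at the sponsor's own assumed low-platelet share.
- Add a note that Z governs and that the rates are illustrative at the assumed control rates.
- In SAP 10.2, replace the description "allocates minimal beta for the first interim analysis" with the allocated beta and the information fraction used. If that is 100/220, the text should give 7.3% for spleen volume and 9.1% for TSS. If the sponsor intended 100/440 (3.6% and 4.5%), the Z boundary would have to be rederived, because 0.18 does not follow from that fraction.

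If 100/220 is confirmed, the cost is four threshold rates corrected wherever they are printed, one table note and one sentence, with no change to the design.

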11. CHANGES AND MODIFICATIONS TO THE ANALYSIS PLAN

All versions of the SAP are listed in Table 8.

Table 8: Statistical Analysis Plan Versions

SAP Version	Date
Original	15 DEC 2020
Amendment 1	26 APR 2022

11.1. Changes to Protocol-Defined Analyses

Not applicable.

11.2. Changes to the Statistical Analysis Plan

11.2.1. Amendment 1

- In Section 4.1.4, the derivation of baseline for participants not treated with any study drug was added.
- In Section 5.3.1, it was clarified that participants with missing baseline assessments will be excluded from the ITT population for the responder analyses.
- In Section 7.1, the combination of DIPSS stratification levels at the time of interim analyses were added.
- In Section 7.3.1 and Section 7.4.2.2, the nonevaluable definitions for the primary endpoint analysis of spleen volume and secondary endpoint analysis of MFSAF TSS, respectively, were added.
- In Section 7.4.2, the window for deriving MFSAF TSS at Week 24 was modified to capture the assessments from the last week before participants return the device.
[REDACTED]
[REDACTED].
- Incorporation of administrative changes. Other minor, administrative changes and changes according to the Protocol Amendment 1 were incorporated throughout the

APPENDIX A. PLANNED TABLES, FIGURES, AND LISTINGS

This appendix provides a list of the planned tables, figures, and listings for the Clinical Study Report. Shells are provided in a separate document for tables that are not in the Standard Safety Tables v1.9.

The lists of tables, figures, and listings are to be used as guidelines. Modifications of the lists that do not otherwise affect the nature of the analysis will not warrant an amendment to the SAP.

Tables

Table No.	Title	Population	Standard
Baseline and Demographic Characteristics			
1.1 Disposition			
1.1.1	Analysis Populations	ITT	X
1.1.2	Summary of Participant Disposition	ITT	X
1.1.3	Summary of Number of Participants Enrolled by Country and Site	ITT	X
1.1.4	Summary of Protocol Deviations	ITT	X
1.2 Demography and Baseline Characteristics			
1.2.1	Summary of Demographics and Baseline Characteristics	ITT	X
1.3 Baseline Disease Characteristics			
1.3.1	Summary of Baseline Disease Characteristics	ITT	
1.3.2	Summary of Myelofibrosis History	ITT	
1.3.3	Summary of Myelofibrosis Screening Symptom Score	ITT	
1.3.4	Summary of Prior Systemic Cancer Therapy by WHO Drug Class and Preferred Term	ITT	X
1.4 Prior Medication and Concomitant Medication			
1.4.1	Summary of Prior Medications	ITT	X
1.4.2	Summary of Concomitant Medications	ITT	X
1.5+ Others			
1.5.1	Summary of General Medical History	ITT	X
Efficacy			
2.1 Primary Efficacy			
2.1.1.1	Cochran-Mantel-Haenszel Test of Proportion of Participants With $\geq 35\%$ Reduction in Spleen Volume at Week 12 and Week 24	ITT	
2.1.1.2	Cochran-Mantel-Haenszel Test of Proportion of Participants With $\geq 35\%$ Reduction in Spleen Volume at Week 12 and Week 24	PP	
2.1.2.1	Cochran-Mantel-Haenszel Test of Proportion of Participants With $\geq 35\%$ Reduction in Spleen Volume at Week 12 and Week 24 – by Sex	ITT	
2.1.2.2	Cochran-Mantel-Haenszel Test of Proportion of Participants With $\geq 35\%$ Reduction in Spleen Volume at Week 12 and Week 24 – by Age Group	ITT	
2.1.2.3	Cochran-Mantel-Haenszel Test of Proportion of Participants With $\geq 35\%$ Reduction in Spleen Volume at Week 12 and Week 24 – by MF Type	ITT	
2.1.2.4	Cochran-Mantel-Haenszel Test of Proportion of Participants With $\geq 35\%$ Reduction in Spleen Volume at Week 12 and Week 24 – by Presence/Absence of V617F Mutation at Baseline	ITT	

Table No.	Title	Population	Standard
2.1.2.5	Cochran-Mantel-Haenszel Test of Proportion of Participants With $\geq 35\%$ Reduction in Spleen Volume at Week 12 and Week 24 – by Presence/Absence of HMR Mutations at Baseline	ITT	
2.1.2.6	Cochran-Mantel-Haenszel Test of Proportion of Participants With $\geq 35\%$ Reduction in Spleen Volume at Week 12 and Week 24 – by Baseline Spleen Volume Group	ITT	
2.1.2.7	Cochran-Mantel-Haenszel Test of Proportion of Participants With $\geq 35\%$ Reduction in Spleen Volume at Week 12 and Week 24 – by Baseline Spleen Palpation Size Group	ITT	
2.1.2.8	Cochran-Mantel-Haenszel Test of Proportion of Participants With $\geq 35\%$ Reduction in Spleen Volume at Week 12 and Week 24 – by Race	ITT	
2.1.2.9	Cochran-Mantel-Haenszel Test of Proportion of Participants With $\geq 35\%$ Reduction in Spleen Volume at Week 12 and Week 24 – by Ethnicity	ITT	
2.1.2.10	Cochran-Mantel-Haenszel Test of Proportion of Participants With $\geq 35\%$ Reduction in Spleen Volume at Week 12 and Week 24 – by Platelet Count	ITT	
2.1.2.11	Cochran-Mantel-Haenszel Test of Proportion of Participants With $\geq 35\%$ Reduction in Spleen Volume at Week 12 and Week 24 – by DIPSS	ITT	
2.2 Secondary Efficacy			
2.2.1.1	Time to the First $\geq 35\%$ Reduction in Spleen Volume	ITT	
2.2.1.2	Duration of Maintenance of a $\geq 35\%$ Reduction in Spleen Volume	ITT With Spleen Volume Response	
2.2.1.3	Time From the First $\geq 35\%$ Reduction in Spleen Volume to Loss of $\geq 35\%$ Reduction in Spleen Volume With a $\geq 25\%$ Spleen Volume Increase From Nadir	ITT With Spleen Volume Response	
2.2.1.4	Summary of Spleen Volume by Visit	ITT	
2.2.2.1	Cochran-Mantel-Haenszel Test of Proportion of Participants With $\geq 50\%$ Reduction in MFSAF v4.0 Total Symptom Score at Week 12 and Week 24	ITT	
2.2.2.2	Cochran-Mantel-Haenszel Test of Proportion of Participants With $\geq 50\%$ Reduction in MFSAF v4.0 Total Symptom Score at Week 12 and Week 24	PP	
2.2.2.3	Time to the First $\geq 50\%$ Reduction in MFSAF v4.0 Total Symptom Score	ITT	
2.2.2.4	Summary of MFSAF v4.0 Total Symptom Score Using 7-Day Window by Visit	ITT	
2.2.2.5.1	Summary of MFSAF v4.0 Individual Symptom Scores by Visit – Fatigue	ITT	
2.2.2.5.2	Summary of MFSAF v4.0 Individual Symptom Scores by Visit – Night Sweats	ITT	
2.2.2.5.3	Summary of MFSAF v4.0 Individual Symptom Scores by Visit – Itchiness	ITT	
2.2.2.5.4	Summary of MFSAF v4.0 Individual Symptom Scores by Visit – Abdominal Discomfort	ITT	

Table No.	Title	Population	Standard
2.2.2.5.5	Summary of MFSAF v4.0 Individual Symptom Scores by Visit – Pain Under Left Ribs	ITT	
2.2.2.5.6	Summary of MFSAF v4.0 Individual Symptom Scores by Visit – Early Satiety	ITT	
2.2.2.5.7	Summary of MFSAF v4.0 Individual Symptom Scores by Visit – Bone Pain	ITT	
2.2.2.6	Summary of MFSAF v4.0 Spleen-Related Symptom Scores by Visit	ITT	
2.2.2.7.1	Overall Survival	ITT	
2.2.2.7.2	Overall Survival	PP	
2.2.2.7.3	Overall Survival Adjusted by Rank Preserving Structural Failure Time	ITT	

Table No.	Title	Population	Standard
Safety			
3.1 Dose Exposure			
3.1.1	Summary of Exposure and Duration of Exposure to Parsaclisib/Placebo	Safety	X
3.1.2	Summary of Exposure and Duration of Exposure to Ruxolitinib	Safety	X
3.1.3.1	Summary of Parsaclisib Compliance	Safety	X
3.1.3.2	Summary of Ruxolitinib Compliance	Safety	X
3.2 Adverse Events			
3.2.1	Overall Summary of Treatment-Emergent Adverse Events	Safety	X
3.2.2	Summary of Treatment-Emergent Adverse Events by MedDRA System Organ Class and Preferred Term	Safety	X
3.2.3	Summary of Treatment-Emergent Adverse Events by MedDRA Preferred Term in Decreasing Order of Frequency	Safety	X
3.2.4	Summary of Treatment-Emergent Adverse Events by MedDRA System Organ Class, Preferred Term, and CTCAE Grade Category	Safety	X
3.2.5	Summary of Grade 3 or Higher Treatment-Emergent Adverse Events by MedDRA System Organ Class and Preferred Term	Safety	X
3.2.6	Summary of Grade 3 or Higher Treatment-Emergent Adverse Events by MedDRA Preferred Term in Decreasing Order of Frequency	Safety	X
3.2.7	Summary of Serious Treatment-Emergent Adverse Events by MedDRA System Organ Class and Preferred Term	Safety	X
3.2.8	Summary of Serious Treatment-Emergent Adverse Events by MedDRA Preferred Term in Decreasing Order of Frequency	Safety	X
3.2.9.1	Summary of Parsaclisib Treatment-Related Treatment-Emergent Adverse Events by MedDRA System Organ Class and Preferred Term	Safety	X
3.2.9.2	Summary of Ruxolitinib Treatment-Related Treatment-Emergent Adverse Events by MedDRA System Organ Class and Preferred Term	Safety	X
3.2.10.1	Summary of Parsaclisib Treatment-Related Treatment-Emergent Adverse Events by MedDRA Preferred Term in Decreasing Order of Frequency	Safety	X
3.2.10.1	Summary of Ruxolitinib Treatment-Related Treatment-Emergent Adverse Events by MedDRA Preferred Term in Decreasing Order of Frequency	Safety	X
3.2.11.1	Summary of Parsaclisib Treatment-Related Treatment-Emergent Adverse Events by MedDRA System Organ Class, Preferred Term, and CTCAE Grade Category	Safety	X
3.2.11.2	Summary of Ruxolitinib Treatment-Related Treatment-Emergent Adverse Events by MedDRA System Organ Class, Preferred Term, and CTCAE Grade Category	Safety	X

Table No.	Title	Population	Standard
3.2.12.1	Summary of Grade 3 or Higher Parsaclisib Treatment-Related Treatment-Emergent Adverse Events by MedDRA System Organ Class and Preferred Term	Safety	X
3.2.12.2	Summary of Grade 3 or Higher Ruxolitinib Treatment-Related Treatment-Emergent Adverse Events by MedDRA System Organ Class and Preferred Term	Safety	X
3.2.13.1	Summary of Parsaclisib Treatment-Related Serious Treatment-Emergent Adverse Events by MedDRA System Organ Class and Preferred Term	Safety	X
3.2.13.2	Summary of Ruxolitinib Treatment-Related Serious Treatment-Emergent Adverse Events by MedDRA System Organ Class and Preferred Term	Safety	X
3.2.14	Summary of Treatment-Emergent Adverse Events With a Fatal Outcome by MedDRA System Organ Class and Preferred Term	Safety	X
3.2.15.1	Summary of Treatment-Emergent Adverse Events Leading to Parsaclisib Dose Reduction by MedDRA System Organ Class and Preferred Term	Safety	X
3.2.15.2	Summary of Treatment-Emergent Adverse Events Leading to Ruxolitinib Dose Reduction by MedDRA System Organ Class and Preferred Term	Safety	X
3.2.16.1	Summary of Treatment-Emergent Adverse Events Leading to Parsaclisib Dose Interruption by MedDRA System Organ Class and Preferred Term	Safety	X
3.2.16.2	Summary of Treatment-Emergent Adverse Events Leading to Ruxolitinib Dose Interruption by MedDRA System Organ Class and Preferred Term	Safety	X
3.2.17.1	Summary of Treatment-Emergent Adverse Events Leading to Discontinuation of Parsaclisib by MedDRA System Organ Class and Preferred Term	Safety	X
3.2.17.2	Summary of Treatment-Emergent Adverse Events Leading to Discontinuation of Ruxolitinib by MedDRA System Organ Class and Preferred Term	Safety	X
3.2.18	Summary of Treatment-Emergent Adverse Events by MedDRA Preferred Term: Life-Table Method	Safety	X
3.2.19	Summary of Treatment-Emergent Adverse Events by MedDRA System Organ Class and Preferred Term: Life-Table Method	Safety	X
3.2.20.1	Summary of Treatment-Emergent Adverse Events of Special Interest by MedDRA Preferred Term	Safety	X
3.2.20.2	Kaplan-Meier Estimates of Time to the First Onset of Treatment-Emergent Adverse Events of Special Interest by MedDRA Preferred Term	Safety	X
3.2.20.3	Kaplan-Meier Estimates of Longest Duration of Treatment-Emergent Adverse Events of Special Interest by MedDRA Preferred Term	Safety	X
